3.3 Patient Selection

3.3.1 Inclusion Criteria

Eligible patients will meet **all** of the following:

1. Have an indication for an ICD implantation or pulse generator change
2. Have documented coronary artery disease. Documented coronary artery disease is defined as having at least one of the following present a) evidence of a prior MI on ECG and/or cardiac enzymes, b) prior revascularization (by coronary artery bypass grafting or percutaneous coronary intervention) c) angina and/or ST-T wave abnormalities indicative of ischemia on exercise stress test, nuclear stress test, or echo stress test, or d) coronary artery disease diagnosed by coronary angiography.
3. Willing and able to comply with protocol requirements, including keeping all required visits
4. Willing to participate in the study and able to sign an IRB approved informed consent form
5. Willing and capable of using Merlin@home.
6. Be at least 18 years of age when enrolled in the study

3.3.2 Exclusion Criteria

Patients will be excluded if they meet **any** of the following:

1. Are pacemaker dependent (defined as a need for ventricular pacing $\geq 20\%$ of the time)
2. Have NYHA Class IV Heart Failure
3. Have persistent or permanent atrial fibrillation
4. Have a known history of intermittent Bundle Branch Block
5. Pregnant or planning a pregnancy during the study participation
6. Have a life expectancy of < 1 year due to any condition
7. Are currently participating in a clinical investigation that includes an active treatment arm

3.4 Device Description

The SJM ICD system is intended to provide ventricular anti-tachycardia pacing and ventricular defibrillation for automated treatment of life-threatening ventricular arrhythmias. AF Suppression™ pacing is indicated for suppression of paroxysmal or persistent atrial fibrillation in patients with the above ICD indication and sinus node dysfunction. In addition, the Investigational Devices have an ST Monitoring Feature that has the ability to detect ST shifts, and to record and store the associated high fidelity IEGMs during those shifts. Refer to the User's Manual for more details.

The pulse generator, along with compatible leads, constitutes the implantable portion of the ICD system.

3.5 Evaluation of Safety

3.5.1 Preliminary Safety Assessment Phase

An initial assessment of the proportion of patients free from complications due to unnecessary procedures resulting from false positive events will be conducted on the first 500 patients to complete 6 months of follow-up.

3.5.2 Primary Endpoint

The primary safety endpoint will evaluate the percentage of patients experiencing false positive events with the use of the ST Monitoring Feature.

3.5.3 Secondary Endpoint

The secondary safety endpoint will evaluate the False Positive Rate (FPR) of the ST Monitoring Feature.

3.6 Evaluation of Efficacy

3.6.1 Primary Endpoint

The primary efficacy endpoint will evaluate the sensitivity of the ST Monitoring Feature to detect clinical events.

4.0 STATISTICAL METHODS

4.1 Randomization and Blinding

This is a prospective, non-randomized, multicenter, pivotal IDE study evaluating the Investigational Devices with the ST Monitoring Feature.

4.2 Data Safety and Monitoring Board

In order to ensure patient safety throughout the study, an independent DSMB will oversee the course of the study. The DSMB will periodically review safety data (percentage of patients with false positive events, False Positive Rate, and study-related adverse events), false negative events, and any procedures/hospitalizations resulting from false positives, even if they do not result in complications. The DSMB will provide a recommendation regarding continuation of the study to the Chairman of the Steering Committee for the study, who will in turn inform the sponsor. A copy of any written communication from the DSMB to the Sponsor regarding recommended changes to the study status, procedures or to the Informed Consent Form will be provided to the FDA during the annual report. If the DSMB recommends substantive changes to the protocol, these communications will be provided along with the applicable IDE supplement. The DSMB will also be informed of the Preliminary Safety Assessment and will be provided with the results when the report is submitted to the FDA. The DSMB will consist of at a minimum 2 cardiologists, 1 electrophysiologist, and 1 statistician. In order to prevent bias, the DSMB committee members will not participate in the study as investigators.

4.3 Analysis of Safety

4.3.1 Preliminary Safety Assessment Phase

An initial assessment of the proportion of patients free from complications due to unnecessary procedures resulting from false positive events will be conducted on the first 500 patients to complete 6 months of follow-up. In patients with an upgraded Fortify[®] ST device, the 6 months of follow-up begins with either their Baseline visit or the Baseline Upgrade visit (during which the firmware upgrade occurs). In patients with Fortify Assura ST[®] and Ellipse ST[®], the 6 months of follow-up begins with the Baseline visit. For those patients with Fortify Assura ST[®] and Ellipse ST[®], the survival time for patients who experience a complication will be calculated as the number of days from the Baseline visit (when the Patient Notifier is activated) to the date of the procedure-related complication. For those patients with Fortify[®] ST devices, the survival time will be calculated as the number of days from either the Baseline visit or the Baseline Upgrade visit (i.e., whichever visit the patient received the firmware upgrade) to the date of the procedure-related complication is first discovered. For patients who withdraw without experiencing a complication prior to analysis, their survival time will be censored at the date of withdrawal. For patients who have not experienced complications at the time of analysis, their survival time will be censored on the date of the analysis.

All patients who have the Patient Notifier turned ON at the Baseline visit or the Baseline Upgrade visit and have completed their 6-month follow up visit or 6 months of follow up since being upgraded will be included in this analysis.

Statistical Analysis Plan

Complications related to unnecessary procedures resulting from false positive events are defined as any procedure-related or test-related complications that occur in a patient in which a Type I ST episode is classified as a false positive according to the criteria described in section 3.2.3. All clinical events will be adjudicated by an independent and blinded Clinical Event Committee for the purposes of determining whether the event was related to ischemia or acute coronary syndrome and whether it was procedure or test related. Complications related to procedures or tests may include, but are not limited to:

- Air embolism
- Allergic reaction to contrast media
- AV fistula
- Bleeding
- Cardiac tamponade
- Contrast nephropathy
- Formation of hematomas or cysts
- Infection
- Myocardial infarction
- Peripheral nerve injury
- Pneumothorax
- Pseudo-aneurysm
- Stent thrombosis
- Stroke
- Thromboemboli
- Venous occlusion
- Venous or cardiac perforation

Analysis

- A Kaplan-Meier estimate of the proportion of patients free from complications arising from a false positive event through the 6 month follow-up visit will be provided with a 95% lower bound on the estimate using Greenwood's formula for the variance of the Kaplan-Meier estimator. If no events have been observed, then a Clopper-Pearson 95% exact lower confidence bound for the proportion of patients free from complications due to unnecessary procedures resulting from false positive events will be provided.
- A tabular presentation of ER visits, doctor office visits, or any medical care will be presented, stratified by false positive, true positive and false negative events.
- The proportion of patients with false positive events, with the count of false positive, true positive and false negative events will be provided. A preliminary estimate of sensitivity will be calculated.
- The proportion of patients with the ST monitoring feature turned off after the Programming and Baseline visits will be tabulated along with the reason for the turning off the ST monitoring feature.
- Baseline demographics and site enrollment will be tabulated.

Statistical Analysis Plan

The above analyses will be presented overall and by the following subgroups:

- Coronary artery disease patients with cardiomyopathy
- Coronary artery disease patients without cardiomyopathy
- Patients with abnormal baseline ECGs, for each of six abnormal subgroup categories
- Patients with normal baseline ECGs
- Patients with arrhythmias
- Gender
- Patients alerted via Merlin.net and patients alerted via device Patient Notifier

Additional Analysis

An analysis will be performed that includes all clinical events using a GEE logit-link linear model to estimate the sensitivity with a working correlation that provides a robust estimator of the variance adjusting for multiple clinical events within patients.

An empirical analysis will be provided for the sensitivity of the ST Monitoring Feature to detect clinical events using the estimator described in the Primary Analysis section. The standard error of this empirical estimate will be calculated as the standard deviation of a bootstrap distribution. The bootstrap distribution will be constructed using 1,000 bootstrap resamples. Each bootstrap resample will be performed at the patient level (in order to preserve the correlation structure of multiple events within one patient, if the occurs), and each resample will have a total sample size equal to the total number of evaluable patients. A two-sided 95% bootstrap confidence interval will be provided.

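### The preliminary safety assessment dates a complication by when it occurred for two device families but by when it was discovered for Fortify ST, though all feed one 6-month estimate

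*Protocol*

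**What the plan says.** Section 4.3.1 (Preliminary Safety Assessment Phase) reads the same in the protocol and the SAP. The assessment "will be conducted on the first 500 patients to complete 6 months of follow-up".

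The survival time is defined separately by device family:

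- **Fortify Assura ST and Ellipse ST:** the "number of days from the Baseline visit (when the Patient Notifier is activated) to the date of the procedure-related complication".
- **Fortify ST:** the start is the Baseline or Baseline Upgrade visit, whichever delivered the firmware upgrade. The time then runs "to the date of the procedure-related complication is first discovered".

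For patients with no complication by the time of analysis, "their survival time will be censored on the date of the analysis". Follow-up can therefore extend past 6 months.

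The main output is "A Kaplan-Meier estimate of the proportion of patients free from complications arising from a false positive event through the 6 month follow-up visit", "with a 95% lower bound on the estimate using" Greenwood's variance. There is a fallback: "If no events have been observed, then a Clopper-Pearson 95% exact lower confidence bound" is given instead. Results are presented overall and for a list of subgroups. Device family is not among them.

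**The concern.** One time-to-event variable has two end dates, and the choice depends on the device model. The firmware upgrade explains why Fortify ST patients may have a different start date. It does not explain a different end date. No reason is given, and no other section of either document brings the two rules together.

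The section's own list of complications includes some that could be found some time after they arise, such as pseudo-aneurysm, AV fistula, infection and venous occlusion. Where that happens around the 6-month point, two patients with the same clinical history fall on different sides of the cut-off because they carry different devices. The error has one direction: a discovery date is never earlier than the date of occurrence, so Fortify ST events can only be moved later, which flatters the 6-month estimate.

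The result goes to the FDA and to the DSMB (section 4.2). If events are few, the dating of a single one is visible in it.

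**Working it through.** The readable text gives no sample-size, power or threshold figure for this assessment, so there is no plan figure to reproduce. The check is a reading of the two rules followed by an illustration using the plan's own estimator.

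**Inputs from section 4.3.1:** n = 500; Kaplan-Meier estimate at 6 months; Greenwood variance when there are events; Clopper-Pearson bound when there are none; censoring at the analysis date.

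**Assumptions, because the documents do not give these:** 6 months taken as day 182; analysis on day 240; no withdrawals before then; 1, 3 or 5 complications in total; bounds read as one-sided, since the plan does not state sidedness.

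**Step 1. One history under each rule.** A complication occurs on day 170 and is found on day 200.

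- Assura/Ellipse rule: event at day 170, before day 182. The estimate is 499/500 = 99.80%.
- Fortify ST rule: event at day 200, after day 182. The estimate is 500/500 = 100.00%, with a Greenwood standard error of 0.

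The event stays on the curve after day 182, but it no longer counts at the time point that is reported.

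**Step 2. Size per event.** With no withdrawals before day 182, the estimate is S = (500 − d)/500, where d is the number of events dated by 6 months. Greenwood's formula then reduces to SE = √[S(1 − S)/500], and the one-sided 95% lower bound is S − 1.645 × SE.

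| Events dated by 6 months | S | SE | One-sided 95% lower bound |
|---|---|---|---|
| 1 | 99.8% | 0.200% | 99.47% |
| 2 | 99.6% | 0.282% | 99.14% |
| 3 | 99.4% | 0.345% | 98.83% |
| 5 | 99.0% | 0.445% | 98.27% |

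Each event moved past 6 months adds 1/500 = 0.2 percentage points to S.

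- 3 complications, 1 shifted: 99.4% to 99.6%; bound 98.83% to 99.14%. Read as two-sided limits, the bound goes from 98.72% to 99.05%.
- 5 complications, 2 shifted: 99.0% to 99.4%; bound 98.27% to 98.83%.

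**Step 3. The zero-event boundary.** With no events the plan switches to Clopper-Pearson: 0.05^(1/500) = 99.40% one-sided, or 0.025^(1/500) = 99.26% two-sided. If the only complication is a shifted one, Greenwood at 6 months gives a degenerate bound of 100%. The fallback is triggered when no events have been observed, and that does not clearly cover an event observed after 6 months. The plan does not say which bound would then be reported.

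**Step 4. Which events are exposed.** Only those that occur by 6 months, in a Fortify ST patient, and are discovered after 6 months but before the analysis. A complication discovered after the analysis is missed for every device.

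**The case against.** The strongest reply is that this is a drafting slip. The Fortify ST sentence is ungrammatical, and without its last three words it matches the other rule. The Assura/Ellipse rule does not mention onset either, so its complication date could be taken as a date of diagnosis or report, and the device difference would then shrink or vanish. This has force: the difference is certain in the wording, but its effect depends on reading the first rule as date of occurrence. It does not remove the need for a correction, because the sentence as it stands is an instruction to the programmer.

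The exposed set is also narrow. Many included patients will have completed a 6-month visit, where an earlier complication would normally be recorded. This stands in part; upgraded Fortify ST patients may qualify instead on 6 months elapsed since the upgrade.

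The consequences are limited. The readable text of section 4.3.1 has no hypothesis or threshold, the CEC reviews all complications (section 3.2.1), and all adverse events are reported (section 4.7.10). This also stands.

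A reader might infer that one missed event inflates the lower bound from 99.05% to 99.40%, by comparing Clopper-Pearson bounds at 1 and 0 events. The plan does not support that comparison, because it uses Clopper-Pearson only with zero events. By its own methods the bounds are 99.47% with one event (Greenwood) and 99.40% with none (Clopper-Pearson), so the bound would fall slightly when the event is lost. In that case the bias shows in the point estimate.

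**Conclusion.** The inconsistency is real and minor. As written, section 4.3.1 can date the same history differently by device, and only later for Fortify ST. Each affected event raises the pooled 6-month estimate by about 0.2 percentage points in 500 patients. The lower bound moves with it while at least one event remains dated by 6 months. These sizes assume 500 patients, no early withdrawals and one-sided bounds, and they read the Assura/Ellipse rule as date of occurrence.

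The total bias cannot be computed: the documents give no device mix, complication rate or discovery lag. It is tempting to assume a lag of a few weeks and state what share of the 6-month window is at risk, but nothing in the documents supports a particular lag. Nor should a reader conclude that complications vanish from the record or that the primary safety or efficacy endpoint is biased. The event remains later on the curve, and this rule belongs to the preliminary assessment only.

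**What to change.** In section 4.3.1 of both documents, use one event date for all devices: the date the complication occurred. Deleting the last three words of "to the date of the procedure-related complication is first discovered" brings the Fortify ST sentence into line. Add two short clauses:

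- when the date of occurrence is unknown, use the earliest documented date of the complication;
- count a complication that occurred by 6 months even if it was found later, provided it was found before the analysis.

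The different start dates for upgraded devices can stay. While the section is open, it would help to say that the zero-event fallback refers to events dated through 6 months.

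The cost is a wording change. The Assura/Ellipse rule already calls for a complication date, so the change extends that requirement to Fortify ST; the earliest-documented-date clause covers cases where it was not captured. Adjudicated onset dating is not needed, and dating onset is not among the CEC's listed tasks. The downside is a slightly less favourable estimate if any such event occurs.

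### The preliminary safety assessment admits only 6-month completers, which conflicts with its own censoring and Kaplan-Meier rules and omits complications followed by death or exit before month 6

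*Protocol*

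**What the plan says.** Section 4.3.1 has the same wording in the Protocol and the SAP. It makes completion a condition of entry twice. The assessment "will be conducted on the first 500 patients to complete 6 months of follow-up", a rule that section 3.5.1 also states. The included patients are then those with the Patient Notifier on at the Baseline or Baseline Upgrade visit who "have completed their 6-month follow up visit or 6 months of follow up since being upgraded will be included in this analysis".

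The same section sets out a time-to-event analysis:

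- Early exits have their own rule: "For patients who withdraw without experiencing a complication prior to analysis, their survival time will be censored at the date of withdrawal".
- Everyone else still free of complications is censored when the analysis is done.
- The estimator is set out as follows: "A Kaplan-Meier estimate of the proportion of patients free from complications arising from a false positive event through the 6 month follow-up visit".
- Its lower 95% limit takes the variance from Greenwood.
- The zero-event case switches method: "If no events have been observed, then a Clopper-Pearson 95% exact lower confidence bound" is given instead.

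The complications listed include cardiac tamponade, myocardial infarction, stroke, stent thrombosis and "Venous or cardiac perforation". The censoring sentences do not mention death. No sentence keeps a patient who has a complication and then dies or leaves before month 6. Section 4.3.2 does write such an exception for the primary safety endpoint: a patient with a false positive who withdraws before the 12-month visit stays in that analysis.

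**The concern.** The cohort is selected on remaining in the study to month 6, and the outcome is freedom from complications over those same 6 months. Some of the listed complications can kill a patient or end participation. A patient who has a false positive, undergoes a procedure, suffers such a complication and is gone before month 6 fails the entry rule and is not counted.

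This matters because the assessment is meant to show whether false alarms lead to harm. Section 4.2 says that it is reported to the FDA and that the results go to the DSMB. The safety endpoints in 4.3.2 and 4.3.3 count false positives, not complications of the procedures that follow them, so they do not supply this proportion. The preliminary false positive proportion and sensitivity tabulated in 4.3.1 would share the selection if they are taken from the same cohort.

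**Working it through.** The plan gives no figure to reproduce. The readable text states 500 patients but no expected complication rate, attrition rate, power or performance goal for this assessment.

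**Step 1: the rules side by side.** Under the entry rule every patient in the cohort has completed 6 months. The withdrawal rule can then act only on withdrawals between month 6 and the analysis date, and these do not affect a 6-month estimate. The reservation "essentially" is needed in one respect, which is why the word is left unquoted in the conclusion: visit windows are not visible, so a 6-month visit might fall slightly before 6 months from Baseline. With no earlier censoring, Kaplan-Meier at 6 months is 1 − k/n for k complications among n completers, and Greenwood's variance is the binomial S(1 − S)/n. If the withdrawal rule was meant for earlier exits, it contradicts the entry rule.

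**Step 2: direction and size.** Let c be the true 6-month complication risk, d the proportion not completing among patients without a complication, and w the proportion not completing among patients with one. All three are assumptions. The risk seen among completers is

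c(1 − w) / [c(1 − w) + (1 − c)(1 − d)].

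For c = 1%, d = 10%, w = 25%: 0.0075 / (0.0075 + 0.891) = 0.83%. For w = 50%: 0.005 / (0.005 + 0.891) = 0.56%.

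| w | Apparent risk, d = 10% | Apparent risk, d = 5% |
|---|---|---|
| 0% | 1.11% | 1.05% |
| 5% | 1.05% | 1.00% |
| 10% | 1.00% | 0.95% |
| 25% | 0.83% | 0.79% |
| 50% | 0.56% | 0.53% |
| 100% | 0% | 0% |

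The true value is 1% throughout. When w = d there is no bias. When w > d the estimate is too favourable, and when w < d it errs the other way, by up to 11% relative at d = 10%. The relative errors are almost the same for c = 0.5% and 2%.

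**Step 3: effect on the bound.** The plan does not say whether the 95% bound is one-sided or two-sided. With no complications among 500 completers, the Clopper-Pearson lower bound is 0.05^(1/500) = 99.40% one-sided, or 0.025^(1/500) = 99.26% if taken from a two-sided interval.

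At an assumed 10% attrition, 500 / 0.9 = 556 patients must start, so 56 lie outside the cohort (11 at 2% attrition, 89 at 15%). Suppose 3 of the 56 had a complication before leaving, and put all 56 back:

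- Other losses censored after the complications: 1 − 3/556 = 99.46%, one-sided Greenwood bound 98.95%.
- Other losses censored before them: 1 − 3/503 = 99.40%, bound 98.84%.

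So the bound would be 98.84% to 98.95%, against the 99.40% reported from completers alone.

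**The case against.** The strongest reply is that this is loose drafting. A withdrawal rule, Kaplan-Meier and Greenwood's variance make little sense unless early leavers were meant to be in the estimate. That may well be the intent. It still leaves two sets of sentences that cannot both be followed, and the withdrawal sentence covers only patients without a complication, so it does not bring back a patient who has one and then leaves.

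A reader might infer that the assessment drops the most severe complications by construction and is therefore biased towards safety. The documents do not support that. A patient with tamponade, stroke or infarction who stays to month 6 is counted, and many listed items, such as bleeding or a contrast reaction, need not end follow-up. A complication that is fatal before month 6 is certainly excluded under the entry rule, but the net direction of bias depends on differential loss, which the documents do not quantify.

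The consequence is also limited. The readable text ties no hypothesis, performance goal or stopping rule to this assessment, and the final sensitivity endpoint in 4.4.1 has no completion requirement. Under 3.2.1 the Clinical Events Committee reviews all deaths and complications. Under 4.2 the DSMB reviews study-related adverse events and procedures or hospitalizations resulting from false positives. These points stand: such events would not go unseen. But neither review changes the estimate.

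**Conclusion.** The concern holds as a conflict between rules with a conditional bias. Read literally, the entry rule turns the 6-month Kaplan-Meier estimate into essentially a proportion of completers and leaves out any complication followed by death or exit before month 6. The result is too favourable only if patients with complications fail to complete more often than others.

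The apparent risks of 0.83%, 0.56% and 0% rest on an assumed 1% true risk, 10% non-completion among other patients, and 25%, 50% or 100% among patients with a complication. They show sensitivity to the rule and do not predict what the trial would find. It would go too far to conclude that the assessment is known to understate harm, or that a regulatory decision rule is compromised, since the readable text contains none. What stands is that the estimate given to the FDA and DSMB has an avoidable selection that the separate reviews do not remove.

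**What to change.** In 3.5.1 and 4.3.1, in both documents:

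- Define the cohort as the first 500 patients, in order of start date, with the Patient Notifier on at the Baseline or Baseline Upgrade visit. Analyse once the last of them has reached, or would have reached, 6 months. Delete the completion requirement.
- Count every complication before month 6 as an event, whatever happens to the patient afterwards.
- Keep the rule that censors complication-free withdrawals at withdrawal.
- Add an explicit rule for deaths without a complication, for example censoring at death, because the present text covers only withdrawal.
- State the Clopper-Pearson denominator for the zero-event case, for example patients with a full 6 months, because the cohort would now include event-free patients with less.
- Report the number of non-completers and their reasons.

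No new data are needed. The cost is that somewhat fewer than 500 patients have a full 6 months, so the bound is slightly wider. At an assumed 10% attrition, 450 patients would have full follow-up, and the one-sided zero-event bound would be 0.05^(1/450) = 99.34% instead of 99.40%.

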3.2.2 Clinical Events

ACS Events

An ACS event is defined as any of the following:

- Death due to a myocardial infarction
- A new Q-wave myocardial infarction on 12-lead ECG
- ST elevation myocardial infarction
- Biomarker evidence of acute myocardial damage*
- Evidence of new plaque rupture by invasive testing (i.e., IVUS) as adjudicated by the blinded Clinical Events Committee
- The presence of TIMI myocardial perfusion grade 0 or 1 consistent with acute injury of the myocardium from embolization
- New surface ECG ST depression or elevation treated with thrombolytic medication

Statistical Analysis Plan

- New surface ECG ST depression or elevation with new or progressive flow-limiting ischemia proven by non-invasive or invasive testing.
- Angiographic stenosis $\geq 70\%$ adjudicated by the blinded Clinical Events Committee as flow-limiting.
- An event that leads to a clinically warranted percutaneous coronary intervention (PCI) or revascularization as determined by the blinded Clinical Events Committee. Clinically warranted is defined as:
 - Angiographically visualized stenosis $\geq 70\%$ correlating with the vascular distribution in which a 12-lead surface ECG documents changes consistent with ischemia or injury in 2 or more contiguous leads
 - Angiographically visualized stenosis $\geq 70\%$ correlating with a vascular distribution shown to have ongoing ischemia by non-invasive stress testing
 - New or progressive angiographically visualized stenosis $\geq 70\%$ correlated with new or progressive anginal symptoms

*NOTE: It is recommended that the “Universal Definition of Myocardial Infarction” proposed by the Joint ESC/ACCF/AHA/WHF in 2007 be used to determine myocardial damage.

Precursor Events

A precursor event is defined as clinical symptoms of an impending ACS event followed by an ACS event within 10 days. Precursor events alone do not meet the ACS event criteria. Multiple precursor events may precede a single ACS. All precursor events will be adjudicated by the Clinical Event Committee (CEC). Symptoms identified as precursors will be grouped with the subsequent ACS event and counted as a single event. Individual precursor events will not be included in the statistical endpoint analysis.

Non Events

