3.2.3 Classification of Events

True Positive (TP): A Type I ST episode detection that occurs up to 72 hours prior to an ACS Event.

False Positive (FP): A Type I ST episode detection that occurs more than 72 hours prior to an ACS Event or that occurs in the absence of a true ACS Event.

True Negative (TN): Absence of a Type I ST episode detection during a Non Event.

False Negative (FN): Absence of a Type I ST episode detection within 72 hours prior to an ACS Event.

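### Section 4.3.1 counts complications by whether the patient has any false positive alarm, so a procedure-caused MI can remove itself from the count while complications unrelated to the alarm are included

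*Protocol*

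**What the plan says.** The protocol and the SAP carry the same text on this point.

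- **Target.** Section 4.3.1 describes the preliminary assessment as the "proportion of patients free from complications due to unnecessary procedures resulting from false positive events". This is causal wording.
- **Operating definition.** The same section defines the complications to be counted: "any procedure-related or test-related complications that occur in a patient in which a Type I ST episode is classified as a false positive", using the classes in section 3.2.3. The list of possible complications includes "Myocardial infarction", stent thrombosis and thromboemboli.
- **Alarm classes.** Under section 3.2.3 a True Positive is "A Type I ST episode detection that occurs up to 72 hours prior to an ACS Event". An alarm is a False Positive if the interval to the ACS Event is longer than that, or if there is no true ACS Event.
- **ACS Events.** The qualifying criteria in section 3.2.2 include "Biomarker evidence of acute myocardial damage" and "The presence of TIMI myocardial perfusion grade 0 or 1 consistent with acute injury of the myocardium from embolization", as well as ST elevation MI and death from MI. None excludes an event caused by a test or procedure.
- **Adjudication.** In section 4.3.1 the CEC has the task of "determining whether the event was related to ischemia or acute coronary syndrome and whether it was procedure or test related". Section 3.2.1 also has it review adverse events of procedures that followed a Type I detection. Neither section 3.2.3 nor the 4.3.1 definition says what these findings do to the class of the alarm.

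**The concern.** The target requires a chain: a false alarm leads to a procedure, and the procedure causes harm. The definition asks only whether the harmed patient has a false positive somewhere in the record. This allows two errors in opposite directions.

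First, the class of an alarm depends on what happens in the next 72 hours, and that can include harm from the procedure the alarm prompted. An MI from that procedure can turn the false alarm into a True Positive and so remove itself from the complication count. Because the class comes from section 3.2.3, the change also reaches the primary safety endpoint (4.3.2), the false positive rate (4.3.3) and sensitivity (4.4.1). Sensitivity would then credit the device with detecting an event that its own alarm led to.

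Second, a complication of a procedure unrelated to the alarm counts if the patient has a false positive at any time, even a later one.

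**Working it through.** The visible text of section 4.3.1 gives no threshold, power or sample size derivation to reproduce. The check therefore applies the written rules to cases and then adds two calculations for scale.

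**Rules applied.** An alarm is a True Positive if an ACS Event follows within 0 to 72 hours, and otherwise a False Positive (3.2.3). A procedure- or test-related complication counts if the patient has at least one False Positive (4.3.1). In cases B to D the CEC is assumed to class the MI as ACS. The alarm is at hour 0 unless stated.

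| Case | Class of alarm | Counted in 4.3.1? |
|---|---|---|
| A. Procedure bleed at 36 h, no ACS | False Positive | Yes |
| B. Procedure-caused MI at 36 h | True Positive | No; a bleed from the same procedure is lost too |
| C. Procedure-caused MI at 96 h | False Positive | Yes |
| D. As B, with another false positive in the patient | True Positive and False Positive | Yes |
| E. Bleed at 3,000 h from an unrelated procedure | False Positive | Yes |
| F. Unrelated procedure complication at 100 h, only alarm at 3,000 h | False Positive | Yes |

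B and C differ only in timing. Under the stated target B should count, and E and F should not.

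**Scale in 4.3.1.** Inputs: the first 500 patients (4.3.1), a one-sided 95% bound and no censoring (the last two are assumptions). The plan uses Clopper-Pearson with no events and Kaplan-Meier with Greenwood's variance otherwise.

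- 0 events: 0.05^(1/500) = 99.40%.
- k events: p = 1 − k/500, and the bound is p − 1.645 × √(p(1 − p)/500).
 - k = 1: 0.998 − 1.645 × 0.001998 = 99.47%.
 - k = 2: 0.996 − 1.645 × 0.002823 = 99.14%.
 - k = 3: 0.994 − 1.645 × 0.003454 = 98.83%.

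Each event moves the estimate by 1/500 = 0.2 percentage points. The bounds for 0 and 1 events come from different methods, so the step between them is not a trend.

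**Scale in sensitivity.** Inputs: a null value of 50% and a 95% Wilson interval (4.4.1), and exactly 41 ACS events (an assumption; the plan requires at least 41 clinical events). With z = 1.96, the lower bound is [p + z²/2n − z√(p(1 − p)/n + z²/4n²)] / (1 + z²/n).

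- 27/41: (0.7054 − 0.1525)/1.0937 = 50.55%, above 50%.
- 26/40, after taking one procedure-caused event out of both numerator and denominator: (0.6980 − 0.1554)/1.0960 = 49.51%, below 50%.

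The smallest count that passes at n = 41 is 27, because 26/41 gives 48.12%. The comparison is therefore a borderline case chosen to show what one event can do.

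**The case against.** The strongest reply is that adjudication is not mechanical. The CEC decides both whether an event is ACS and whether it is procedure related, and the false positive rule speaks of a true ACS Event. A sensible committee could decline to class a procedure-caused MI as ACS. This stands in part: nothing forces the cancellation. But nothing prevents it either. The two findings are not stated to be mutually exclusive, and no rule lets the second override the first.

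A reader might infer that the most serious harms of false alarms are removed as a matter of course. The documents do not support that. Stroke, tamponade, perforation and bleeding are not ACS criteria and remain counted, unless the same procedure also causes an ACS Event in the window. An MI after 72 hours remains counted. Stent thrombosis is a weak example: a stent placed within the window for a stenosis that meets section 3.2.2 already makes the alarm a legitimate True Positive.

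The harms also stay visible elsewhere. The CEC reviews all deaths and complications (3.2.1), the DSMB sees study-related adverse events (4.2), medical care is tabulated by alarm class (4.3.1), and all adverse events are summarized (4.7.10). What is at risk is the 4.3.1 estimate and the endpoint classification, not all safety oversight.

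On over-counting, the surrounding text of 4.3.1 is causal, so the intent is clear, and the error is conservative for safety. That softens this half of the point, but the definition still does not say what its target says.

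**Conclusion.** The point holds: the rules are wrong as written and should be fixed. Cancellation needs three conditions together: the procedure-caused event falls within 72 hours after the alarm, the CEC classes it as ACS, and the patient has no other false positive. When all three are met, the complication and any other from that procedure leave the 4.3.1 count, the patient leaves the 15% count, and sensitivity gains a True Positive. The gain in sensitivity needs only the first two.

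The documents do not give the frequency of such events. The two errors in 4.3.1 run in opposite directions, so its net bias is unknown. A reader might conclude that 4.3.1 is biased in the device's favour or would reach a wrong pass or fail; neither can be shown, the second because no threshold is visible. The clearest consequence is for sensitivity, where one such event could reverse a borderline result (50.55% against 49.51%, assuming exactly 41 ACS events). The 14-day re-analysis in 4.7.15 lengthens the window in which the same thing can happen.

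**What to change.** 1. **Section 4.3.1.** Count a complication only if the test or procedure was performed because of a Type I episode that is classed as a False Positive after applying item 2.
2. **Section 3.2.3.** State that an event the CEC judges to be caused by a test or procedure performed because of a Type I episode cannot make that episode a True Positive. Exclude that event from both the numerator and the denominator of sensitivity in 4.4.1; left in the denominator, it would count against the device without being a fair test of detection. ACS findings that the procedure reveals but did not cause, such as flow-limiting stenosis or plaque rupture, still qualify. A rule based on whether ACS was established before the procedure began would not work, because these findings are made during it.
3. **Section 3.2.1.** Have the CEC record which alarm prompted the procedure, as part of its existing relationship review.

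Sections 4.3.2 and 4.3.3 restate the false positive rule in their own words, so they should refer to the revised 3.2.3. Make the same changes in the protocol and the SAP.

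The cost is wording and a small extra CEC recording task. Some alarms may move from True to False Positive, which would make the reported results slightly less favourable.
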